4.11.2 Deaths, Serious Adverse Events, and Adverse Events of Special Interest

A by-participant listing of death, adverse of special interest (AESI) and all serious adverse events will be created.

4.11.3 Clinical Laboratory Evaluation

The following safety laboratory parameters will be measured:

Hematology: Hematocrit, Hemoglobin, Platelet count, Red blood cell count, White blood cell count with differential, Neutrophils, Eosinophils, Basophils, Monocytes, Lymphocytes, Activated partial, thromboplastin time.

Clinical Chemistry: Albumin, Alkaline phosphatase, Alanine aminotransferase, Aspartate aminotransferase, Bilirubin (total and conjugated), C-reactive protein, Calcium, Chloride, Creatinine, Creatine phosphokinase, Gamma-glutamyl transferase, Glucose, Potassium, Sodium, Total cholesterol, Total protein, Triglycerides, Tryptase, WOCBP Only (per SoA): Human chorionic, gonadotropin.

Viral Serology: Hepatitis B surface antigen, Hepatitis B core antigen antibody, Hepatitis C virus antibody, HIV antibody (HIV1 and HIV2), COVID-19, Tuberculosis (quantiFERON Gold™ test).

Urinalysis: Protein, Glucose, Red blood cells, White blood cells, Ketone bodies, pH.

At discretion of Investigator based on urinalysis results:

- Microbiology
- Urine microscopy

Drugs of Abuse: Alcohol, Amphetamines/methamphetamines, Barbiturates, Benzodiazepines, Cannabinoids, Cocaine, Opiates.

Individual data listings of all the laboratory results will be presented for each participant. Flags will be attached to values outside of the laboratory's reference limits along with the investigator's assessment. Clinically significant laboratory test abnormalities that were considered adverse events by the investigator will be presented in the adverse event listings.

Any laboratory parameters with results from the laboratory given as '<xx' or '>xx' in the database will be imputed with the absolute value of the number without the sign (e.g., < 9.2 will be imputed as 9.2) for the descriptive statistics and changes from baseline.

Safety laboratory tests (observed values and change from baseline) will be summarized descriptively in tabular format by dose cohort and pooled placebo group. The baseline for the laboratory parameters will be the measurement obtained prior to administration of IV of XTMAB-16. .

In order to compare a before-and-after effect for selected laboratory parameters, shift tables with regards to reference ranges will be provided for each dose step, and for all participants.

The number and percentage of participants with newly occurring liver enzyme abnormalities occurring at any time post-baseline will be summarized by dose cohort and by overall.

4.11.4 Vital Signs, Physical Findings and Other Observations Related to Safety

Vital Signs

Oral, tympanic or temporal body temperature, respiratory rate, pulse, and systolic and diastolic blood pressure will be assessed.

Vital signs data will be listed by participant including changes from baseline. The baseline for the vital signs' measurements will be the measurement obtained prior to administration of IV of XTMAB-16.

Table 7 Grading for Vital Signs

Vital Signs *	Mild (Grade 1)	Moderate(Grade 2)	Severe (Grade 3)	Potentially Life Threatening (Grade 4)
Fever (°C) ** (°F) **	38.0 – 38.4 100.4 – 101.1	38.5 – 38.9 101.2 – 102.0	39.0 – 40 102.1 – 104	> 40 > 104
Tachycardia - beats per minute	101 – 115	116 – 130	> 130	ER visit or hospitalization for arrhythmia
Bradycardia - beats per minute***	50 – 54	45 – 49	< 45	ER visit or hospitalization for arrhythmia
Hypertension (systolic) - mm Hg	141 – 150	151 – 155	> 155	ER visit or hospitalization for malignant hypertension
Hypertension (diastolic) - mm Hg	91 – 95	96 – 100	> 100	ER visit or hospitalization for malignant hypertension
Hypotension (systolic) – mm Hg	85 – 89	80 – 84	< 80	ER visit or hospitalization for hypotensive shock
Respiratory Rate – breaths per minute	17 – 20	21 – 25	> 25	Intubation

* Subject should be at rest for all vital sign measurements.

** Oral temperature; no recent hot or cold beverages or smoking.

*** When resting heart rate is between 60 – 100 beats per minute. Use clinical judgement when characterizing bradycardia among some healthy subject populations, for example, conditioned athletes.

Toxicity grading of vital signs will be summarized by dose cohort.

Descriptive statistics (n, mean, SD, median, minimum, maximum) for absolute values and changes from baseline will be presented by dose cohort.

ECG

Standard safety 12-lead ECGs will be performed as shown in the Schedule of Assessments.

The following ECG parameters will be recorded:

P wave, QRS complex, U wave, QRS duration, QT interval, QTcF, T wave, ST segment, RR interval, PR interval, and qualitative results.

The ECG will be evaluated by the Investigator as 'Normal', 'Abnormal, NCS' or 'Abnormal, CS'.

All ECG parameters will be listed by participant for each dose cohort and time point including changes from baseline. The baseline for the ECG measurements will be obtained prior to administration of IV of XTMAB-16.

Descriptive statistics (n, mean, SD, median, lower quartile, upper quartile, minimum, maximum) for absolute values and changes from baseline will be presented by dose cohort and pooled placebo group. A categorical QTc analysis will also be performed.

A summary of the number and percentage of participants with QTcF intervals exceeding some predefined upper limits (e.g. >450ms, >480ms, >500ms for measured values as well as. >30ms, >60ms for changes from baseline) of ECG parameters will be displayed in a frequency table.

Mean QTcF values (\pm SD) over time per dose and pooled placebo will be presented graphically on Safety set.

If findings on telemetry are identified, a further concentration QT analysis (tie-matched QT and QTc analysis for XTMAB-16 and placebo) **may** be further evaluated. ER analysis consists of the following:

1. A linear mixed effects model with Δ QTcF as the dependent variable, drug plasma concentration as a continuous covariate, treatment (active or placebo) as categorical factor, and a random intercept for each participant. Note: concentration values are set to 0 for placebo participants.
2. The predicted mean $\Delta\Delta$ QTcF (placebo corrected, change from baseline) at the observed geometric mean Cmax (i.e., the product with the slope estimate treatment effect [active – placebo]) will be calculated. Two-sided 90% CIs of the estimate will be calculated using a bias-corrected nonparametric bootstrap with 1,000 resamples and participant as the unit of resampling. Note: Bootstrap is used to provide robust estimate for the 90% CI. Resampling will be done independently for the active and the placebo participants. For each resample, the model will be fitted and the predicted mean $\Delta\Delta$ QTcF will be computed at the geometric mean Cmax determined from the resampled data. The 90% CI will be determined from the distribution of resampled predicted values.
3. Decisions to classify the risk QTprolongation induced by XTMAB-16, the upper bound of the two-sided 90% CI for the $\Delta\Delta$ QTcF effect of XTMAB-16 as estimated by ER model should be <10ms at the observed geometric mean Cmax to exclude a risk QT prolongation induced by XTMAB-16. (reference: ICH E14 Guideline: The Clinical Evaluation of QT/QTc Interval Prolongation and Proarrhythmic Potential for Non-Antiarrhythmic Drugs Questions & Answers (R3))

Physical Examination

- A complete physical examination will include assessments of general appearance, skin; head/neck; pulmonary, cardiovascular, gastrointestinal, external genitourinary (optional), lymphatic, and musculoskeletal systems; extremities; eyes (inspection and vision control); ears, nose; throat; and neurologic status.
- An abbreviated physical examination will include assessments of general appearance; head, ears, eyes, nose, and throat; cardiovascular; respiratory; and gastrointestinal systems (including the abdomen).
- A targeted physical examination may be conducted at any time at the Investigator's discretion and should be limited to systems of clinical relevance (ie, cardiovascular, respiratory, lymph nodes, liver.)

Abnormal physical examination findings will be listed.

Assessment of liver-related changes will include:

- 3 \times -, 5 \times -, 10 \times -, and 20 \times ULN elevations of AST, ALT, and either ALT or AST
- Any elevations of bilirubin: elevated total bilirubin to $>2 \times$ ULN
- Any elevations of ALP $>1.5 \times$ ULN
- Elevation of AST or ALT ($>3 \times$ ULN) accompanied by elevated bilirubin ($>1.5 \times$ ULN, $>2 \times$ ULN)
- Elevation of AST or ALT in temporal association with nausea, vomiting, anorexia, abdominal pain, or fatigue

- Any liver-related deaths and liver-related treatment discontinuations.

Assessment of liver-related changes will be summarized.

4.11.5 Safety Monitoring (Independent Data Monitoring Committee [IDMC], Data Monitoring Committee [DMC], Data and Safety Monitoring Board [DSMB])

Not Applicable.

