- k Single 12-Lead ECGs will be collected at all time points. Additional ECGs will be performed at the discretion of the Investigator. Telemetry recording will begin on Day -1 and continue through 50 hours after the start of infusion. At specified time points, for extraction of telemetry data, participants should be in a semi-reclined resting position for at least 10 minutes prior to the target time of data extraction (at least 15 minutes when coinciding with PK/ADA/nAb blood collection). On Day -1, resting periods for telemetry data extraction should occur at 1, 2, 3, and 8 hours (corresponding to the projected time points on Day 1). On Day 1, resting periods for telemetry data extraction should occur at predose (to match the time point for 24 hours after the start of infusion) and 1, 2, 3, 8, and 24 hours after the start of infusion. A resting period for telemetry data extraction will also occur at 50 hours after the end of infusion. During infusion, data will be collected in a semi-supine/semi-reclined position, and for all other readings, data will be collected in a supine position.
- l Tryptase levels will be assessed at Baseline for all participants. For any participant who experiences anaphylaxis within 4 hours after the end of infusion, and additional sample for assessment of tryptase levels should be collected as soon as is reasonable. See [Appendix 5](#) for diagnosis and treatment of anaphylaxis.

- m Blood samples for PK/ADA/nAb will be collected for analysis from participants who experience an SAE that is also considered related to study treatment.

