### 3 OBJECTIVES AND ENDPOINTS

OBJECTIVES	ENDPOINTS	JUSTIFICATION FOR ENDPOINTS
To evaluate the safety, tolerability, immunogenicity, PK, and selected clinical biomarkers after a single IV infusion of XTMAB-16 at 2 and 4 mg/kg doses in normal healthy participants.	
Safety and Tolerability
 
The incidence of treatment-emergent adverse events (TEAEs) and serious adverse events (SAEs)
 
Observed values and change from Baseline in safety laboratory tests (hematology, clinical chemistry, urinalysis) by visit
 
Observed values and change from Baseline in ECG by visit
 
Time-matched Baseline and 50-hr postdose digital ECG monitoring
 
Observed values and change from Baseline in vital signs
 
Immunogenicity
 
Number and percentage of participants by cohort who test positive for XTMAB-16 ADA at Baseline, Day 29, Day 57, and Day 71
 
Number and percentage of participants by cohort who test positive for XTMAB-16 nAb at Baseline, Day 29, Day 57, and Day 71
 
Pharmacokinetics
 
Maximum observed XTMAB-16 concentration (<math>C_{max}</math>)
 
XTMAB-16 serum concentration at the end of drug infusion (<math>C_T</math>)
 
Time to maximum observed XTMAB-16 concentration (<math>t_{max}</math>)
 
Area under the XTMAB-16 concentration-time curve from time zero (predose) extrapolated to infinity (<math>AUC_{0-\infty}</math>)
	The endpoints chosen for this study are standard and commonly accepted for Phase 1 FIH trials to establish initial safety, PK, and immunogenicity in the support of continued investigation of the study drug for clinical development.

OBJECTIVES	ENDPOINTS	JUSTIFICATION FOR ENDPOINTS
	
Area under the XTMAB-16 concentration-time-curve from time zero to (predose) to the last quantifiable time point at <math>t</math> (<math>AUC_{0-t}</math>)
 
Systemic clearance after IV dosing (CL)
 
Apparent terminal half-life (<math>t_{1/2}</math>)
 
Volume of distribution following IV dosing (<math>V_z</math>)
 
Mean residence time (MRT)
 
Biomarkers
 
Absolute and percent change from Baseline in the following biomarkers
 

• Angiotensin converting enzyme (ACE)

• soluble IL-2 receptor (sIL-2R)

• Interleukin 6 (IL-6)

• soluble TNF<math>\alpha</math> (sTNF<math>\alpha</math>)

	

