### 9.4 STATISTICAL ANALYSES

Statistical analysis and generation of tables, figures, study participant data listings, and statistical output will be performed using SAS® Version 9.4 or higher.

All original and derived parameters will be listed and described using summary statistics. For continuous parameters, number of participants with available measurements, mean, standard deviation (SD), median, minimum, and maximum and for categorical parameters, number of participants and percentages (to 1 decimal place) in each category will be presented.

All descriptive statistics will be presented by treatment where applicable (eg, biomarkers), including columns for all treated participants and all participants on demographics, baseline characteristics, and AE displays, and using the available data for the study population as observed. Summaries of concentration data will be based on geometric mean and geometric SD instead of arithmetic versions. All tabulations will be sorted by treatment, parameter, and Day (including time relative to dosing if applicable, unless otherwise stated). Only scheduled visits and times relative to dosing will be included in the tabulation.

Categorical data will be summarized by Day/Week/Time and treatment.

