#### 9.4.2 SAFETY ANALYSES

##### 9.4.2.1 LABORATORY EVALUATIONS, VITAL SIGNS AND ECG

Laboratory evaluations, vital signs, and ECGs will be analyzed for the Safety Set for observed cases. Descriptive statistics will be presented by cohort and treatment at each time point: change from Baseline in vital signs, serum chemistry, hematology, and urinalysis. For laboratory data, changes between the Baseline or, if missing, screening value and each posttreatment assessment may be presented in shift tables or using other summaries as detailed in the SAP. Assessment of liver-related changes will include:

- 3  $\times$ -, 5  $\times$ -, 10  $\times$ -, and 20  $\times$  ULN elevations of AST, ALT, and either ALT or AST
- Any elevations of bilirubin: elevated total bilirubin to  $>2 \times$  ULN
- Any elevations of ALP  $>1.5 \times$  ULN
- Elevation of AST or ALT ( $>3 \times$  ULN) accompanied by elevated bilirubin ( $>1.5 \times$  ULN,  $>2 \times$  ULN)
- Elevation of AST or ALT in temporal association with nausea, vomiting, anorexia, abdominal pain, or fatigue
- Any liver-related deaths and liver-related treatment discontinuations.

For ECG parameters, descriptive analysis and shift tables from predose will be performed. Further concentration QT analysis (eg, time-matched QT, and QTc analyses for XTMAB-16 and

placebo may be evaluated, including effect of XTMAB-16 concentration on QTc, and categorical analyses) and will be defined in a finalized SAP.

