3.2 Endpoints and Associated Variables

3.2.1 Primary Endpoints

Safety and Tolerability

- The incidence of treatment-emergent adverse events (TEAEs) and serious adverse events (SAEs).
- Observed values and change from Baseline in safety laboratory tests (hematology, clinical chemistry, urinalysis) by visit.
- Observed values and change from Baseline in ECG parameters by visit.
- Time-matched Baseline and 50-hr post dose digital ECG parameters monitoring.
- Observed values and change from Baseline in vital signs.

Immunogenicity

- Number and percentage of participants by cohort who test positive for XTMAB-16 anti-drug antibody (ADA) at Baseline, Day 29, Day 57, and Day 71
- Number and percentage of participants by cohort who test positive for XTMAB-16 neutralizing antibody (nAb) at Baseline, Day 29, Day 57, and Day 71

Biomarkers

Absolute and percent change from Baseline in the following biomarkers:

- Angiotensin converting enzyme (ACE)
- soluble IL-2 receptor (sIL-2R)
- Interleukin 6 (IL-6)
- soluble TNF α (sTNF α)

Other relevant biomarkers may be assessed to better understand PK/PD relationships.

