4.2 General Presentation Considerations

This section is applicable to all non-PK assessments.

TLF outputs will be generated for XTMAB-16 and pooled placebo by the planned treatment duration.

The participants, who received “Placebo” in each cohort, will be pooled into a single placebo group (Pooled Placebo) in each respective part for all summaries and presentation related to safety for this study. The PK outputs will be generated for each XTMAB-16 dose.

‘Baseline’ is defined as the last observed value of the parameter of interest prior to dosing (this includes unscheduled visits) for each XTMAB-16 dose and pooled placebo group. ‘End of Study’ for a participant is defined as the last available post-treatment assessment. ‘Study Day’ will be calculated relative to the date of randomization i.e. Study Day = Assessment Date -Randomization Date + 1.

In case of any unscheduled repeated assessments occurred during the period, the following rule will be applied, unless specified otherwise:

If unscheduled repeated measurement of a specific parameter occurs prior to the first XTMAB-16 administration (Day 1), then the last obtained value prior to dosing will be considered in the descriptive statistics and in the calculation of change from baseline.

If unscheduled repeated measurement of a specific parameter occurs after Day 1 or XTMAB-16 or Placebo administration, then the first (non-missing) value after dosing will be used in descriptive statistics and in the calculation of change from baseline.

All data will be listed according to the number of decimal places presented in the source data with a limitation on maximum of 3 decimal places. Continuous data will be summarized in terms of the mean, standard deviation (SD), median, minimum, maximum and number of observations, unless otherwise stated.

The minimum and maximum will be reported to the same number of decimal places as the raw data recorded in the database. The mean and median will be reported to one more decimal place than the raw data recorded in the database. The SD will be reported to two more decimal places than the raw data recorded in the database. In general, the maximum number of decimal places reported shall be four for any summary statistic.

Departure from these general rules will be specified in the output shell document.

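### The SAP lists a time-matched digital-ECG endpoint as primary but commits to no time-matched analysis; footnote k conflicts on the 50-hour reading, and the optional QTc rule names no dose for Cmax

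*SAP*

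**What the plan says.** **Endpoint.** SAP 3.2.1 lists "Time-matched Baseline and 50-hr post dose digital ECG parameters monitoring" under primary endpoints. Protocol section 3 has the same item, "Time-matched Baseline and 50-hr postdose digital ECG monitoring", without ranking it.

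**Readings.** Footnote k of the schedule of assessments provides the matches: "On Day -1, resting periods for telemetry data extraction should occur at 1, 2, 3, and 8 hours". It adds a Day 1 predose reading as the match for 24 h. Post-dose extractions fall at 1, 2, 3, 8 and 24 h from the start of infusion, with one more at 50 h. Footnote k runs telemetry to 50 h after the start of infusion but places that last extraction 50 h after the end. The SAP's copy of the footnote says the same.

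**Analysis.** For the 12-lead ECGs, SAP 4.11.4 commits to listings, descriptive statistics of values and changes, a categorical QTc table and a mean QTcF plot. Time matching appears only in the sentence that begins "If findings on telemetry are identified, a further concentration QT analysis", and there the verb is *may*. Protocol 9.4.2.1 is equally permissive: time-matched analyses for XTMAB-16 and "placebo may be evaluated, including effect of XTMAB-16 concentration on QTc".

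**Baseline.** Under SAP 4.2, baseline "is defined as the last observed value of the parameter of interest prior to dosing". SAP 4.11.4 adds: "The baseline for the ECG measurements will be obtained prior to administration of IV of XTMAB-16".

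**Optional model.** SAP 4.11.4 models change in QTcF on concentration, with an active-or-placebo factor and a random intercept. It predicts the placebo-corrected change at the observed geometric mean Cmax and bootstraps a two-sided 90% interval, resampling active and placebo participants separately. A QT risk is excluded if the upper bound is below 10 ms.

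**The concern.** Day -1 readings are collected so that each post-dose QTcF can be compared with a drug-free value at the same clock time. If the analysis that uses them depends on an undefined trigger and then on discretion, a listed endpoint may have no time-matched result, and whether it has one could be decided after the data are seen. The 50-h reading is the one named in the endpoint's title. Under one sentence of footnote k it falls after recording has stopped. If the concentration-QTc model is run, the SAP attaches a yes-or-no classification to it while leaving open the exposure at which the bound is read.

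**Working it through.** The plan gives no figure to reproduce here: there is no power or precision calculation, and none is needed for these checks.

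**1. What is committed.** The committed ECG outputs in SAP 4.11.4 concern the standard 12-lead recordings. With the SAP 4.2 baseline, every post-dose change is taken from one last pre-dose value. No committed output uses the four Day -1 extractions. The two provisions that mention time matching (SAP 4.11.4 and protocol 9.4.2.1) are both optional.

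**2. Matches named in the visible text** (footnote k; the body of protocol Table 8 is not visible):

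| Post-dose extraction | Baseline reading named |
|---|---|
| 1, 2, 3, 8 h | Day -1, same hour |
| 24 h | Day 1 predose |
| 50-h reading | none |

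That is 5 of 6.

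**3. Timing of the 50-h reading.** The infusion lasts 2 h (protocol synopsis, SAP section 1).
- 50 h after the end = 50 + 2 = 52 h from the start, which is 2 h after the stated end of recording. Protocol 6.1.2 makes 2 h the minimum duration, so the gap is at least 2 h.
- Protocol 8.2.4 ends telemetry 50 h after the start. Table 8 footnote a and the schedule header also count from the start.
- Clock time: 50 − 48 = 2, which is a Day -1 slot; 52 − 48 = 4, which is not among 1, 2, 3 and 8.

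**4. Where the 10 ms rule is read.** Inputs: projected Cmax of 47.8 µg/mL (2 mg/kg) and 95.7 µg/mL (4 mg/kg) from protocol Table 3, and 9 active participants per cohort.
- Pooled geometric mean = √(47.8 × 95.7) = 67.6 µg/mL.
- Against 4 mg/kg: 67.6/95.7 − 1 = −29%. Against 2 mg/kg: 67.6/47.8 − 1 = +41%.
- Illustration, assuming a pure slope effect of 10 ms at 95.7 µg/mL: the pooled prediction is 10 × 67.6/95.7 = 7.1 ms, and at 2 mg/kg it is 10 × 47.8/95.7 = 5.0 ms.

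**5. Resampling without regard to dose.** Draw 18 active participants with replacement from 9 + 9. The number k on 4 mg/kg is Binomial(18, 0.5), and its 5th and 95th percentiles are 6 and 12.
- Geometric mean = 47.8^((18−k)/18) × 95.7^(k/18).
- k = 6 gives 60.2; k = 9 gives 67.6; k = 12 gives 75.9 µg/mL.
- On the same pure-slope illustration: 10 × 60.2/95.7 = 6.3 ms and 10 × 75.9/95.7 = 7.9 ms.

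This movement comes from dose mix alone. It treats each projected value as every participant's Cmax, so between-participant spread would widen it.

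**The case against.** The best defence is that the optionality is deliberate. The protocol uses *may* as well, and the SAP's revision history records a clarification of the exposure-response QT analysis. The endpoint promises monitoring, while the neighbouring ECG bullet promises values and changes. No hypothesis is tested, and SAP 3.2.1 places all safety, immunogenicity and biomarker items under primary, so the label carries little weight. Protocol 9.4 also states: "All original and derived parameters will be listed and described using summary statistics". This removes one tempting inference, that the telemetry readings will go unreported. They may well be listed and summarised. But that sentence neither defines nor requires a time-matched change, so the main point stands.

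On footnote k, a slip of one word is plausible, since most other references count from the start. The two sentences still conflict in both documents and need reconciling.

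On the model, a reader might infer two further defects that the documents do not support:
- *The prediction formula is undefined.* The parenthesis about the slope and treatment effect is garbled, possibly through text extraction. But the stated model, with concentration set to 0 for placebo, already implies treatment effect + slope × Cmax.
- *The SAP's ECG baseline rules out time matching.* The 4.11.4 sentence asks only for a value before administration, which Day -1 readings satisfy. The sentence introducing the model says time-matched (misspelt), and protocol 9.4.1 lets a specific provision override its general baseline. Only the last-observed-value rule in SAP 4.2 pulls the other way.

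For Cmax, one can answer that SAP 4.2 produces PK outputs per dose. But the bootstrap takes the geometric mean from resampled active participants as one group, so the two passages point to different readings and neither is stated.

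**Conclusion.** The point holds in three parts, and the first carries most weight.

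1. Neither document commits to a time-matched change for an endpoint the SAP calls primary. None of the four Day -1 readings enters a committed time-matched analysis.
2. Footnote k contradicts itself by 2 h in both documents. Followed literally, the last extraction falls after recording ends. The visible text names no baseline match for that reading. It would go too far to say that none exists, because the body of Table 8 cannot be seen.
3. If the optional model is run, the exposure at which the 10 ms bound is read is not fixed. On projected Cmax the candidates are 47.8, 67.6 and 95.7 µg/mL. Under the pooled reading, dose mix alone moves the point over about 60 to 76 µg/mL (central 90%).

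The third part rests on projected, not observed, Cmax. The millisecond figures assume a pure slope effect. The effect on interval width was not estimated, since the documents give no QTcF variability. Nothing here implies that the trial is invalid or that participants are at added risk. These are gaps that should be closed before unblinding.

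**What to change.** 1. In SAP 4.11.4, commit to a table of time-matched change in QTcF at each extraction time, by dose and pooled placebo, without the telemetry-findings trigger. Name the baseline reading for each time, including the 50-h reading.
2. Reconcile the two 50-h references in footnote k (protocol and SAP) with each other, with protocol 8.2.4 and with Table 8 footnote a.
3. If the concentration-QTc model is run, resample within each dose group and placebo, report the 90% interval at each dose's geometric mean Cmax, and state that the 10 ms rule is read at the higher dose's exposure.
4. As minor clarifications, state that change in QTcF in the model uses the time-matched baseline, overriding SAP 4.2, and write the prediction as treatment effect + slope × Cmax.

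The cost is one extra table from readings already scheduled, a few SAP sentences and a corrected footnote. The downside is a 10 ms bound that may be less favourable at the higher exposure.
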